## Study Protocol and Statistical Analysis Plan

We propose investigation into the efficacy of sleep hygiene interventions on Americans ages 50-80. This will be done by examining the effectiveness of two separate interventions on improving sleep hygiene habits and physiological markers of sleep provided by wearable technology on sleep efficiency, time in bed, time actually sleeping, and time spent at each stage of sleep. The proposed research project will evaluate the efficacy of sleep hygiene education on CDOA and assess the ability of daily automated text messaging in CDOA to serve as an effective augmentation for sleep hygiene education. This research topic corresponds to the South Dakota Biomedical Research Infrastructure Network (BRIN) area of focus: "Physiological (including cellular) and developmental responses to stimuli." Physiological markers of sleep provided by wearable technology on sleep efficiency, time in bed, time actually sleeping, and time spent at each stage of sleep.

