### *Research Plan*

#### **Specific Aim 1: Evaluate the efficacy and feasibility of sleep hygiene education on CDOA.**

Rationale: Our first aim is to determine if sleep hygiene education can be beneficial in improving sleep health in the CDOA population. Sleep hygiene education has been shown to be effective in university students, high school students, athletes, and working adults, but up until very recently has yet to be shown in CDOA. Recently, Tucker et al. published a pilot study looking at virtual sleep health education in older adults and found significant changes in sleep quality, maladaptive sleep health behaviors, and daytime sleepiness compared to controls. In this six-week study, six 30-minute videos were used to educate participants on sleep health.[23] A variety of other sleep hygiene education tools have been used to assist in improving sleep health in younger populations, but a one-time educational video was chosen for this project as this was the most popular intervention in previous studies and because we wanted to explore if a one-time educational video would show similar findings as the recent 6-week Tucker et al. study had in regard to sleep health behavior change.[5, 23] Therefore, a 4-week, home-based, technology-supported program targeting sleep hygiene will be conducted among 80 CDOA, ages 50-80 using a 30-minute educational video. Eighty participants is based off of the systematic review performed by Murawski et al. which reviewed sleep health intervention research studies which had participant sizes ranging from 19 to 391 with a median of 84.[5] Taking into account a potential dropout rate of 20%, the initial total number of participants to be recruited will be 100. Similar studies performed in younger populations have shown 4-weeks is an effective time frame to implement sleep hygiene education. This in combination from data from the Murawski review which showed an average study duration of 5-weeks with a mode of 4-weeks, therefore 4-weeks was chosen for our study duration.[5] During the 4-week study, several physiological markers will be taken. These markers will be taken from data collected on the FitBit Inspire HR device and will include sleep efficiency, time in bed, time actually sleeping, sleep midpoint, and time spent at each stage of sleep. FitBit was the device chosen to track these markers due to its efficacy and comparability to the Actigraph device along with FitBit's usability.[32] Of the several wearable devices that track sleep on the market, FitBit is used in more biomedical clinical research than any other consumer wearable.[33] The FitBit Inspire HR 2 was specifically chosen given its ability to track sleep along with it aligning most closely with

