
the FitBit Alta (now out of stock with FitBit) that was proven comparable and slightly more accurate to actigraphy as researched by Chinoy et al. in 2020.[30]

Experimental design: The proposed 3-year pilot study will begin in the fall (September 2022) and conclude before the end of the academic year (May 2025). This proposal design outlines the first year of this 3-year study. The first step in the experimental process will be the creation of a 30-minute sleep hygiene education video that will be provided to participants to watch on either a smartphone or computer. The video will be created by the PI and student researcher(s) and reviewed and modified based on feedback from the mentors. This video will include tips to improve sleep hygiene and habits. The video will provide education on the value of having a consistent time of going to sleep and waking up in the morning, setting the bedroom up so that it is a comfortable temperature, dark, quiet, and relaxing. The video will also include information regarding the value of removing electronic devices from the bedroom, the importance of exercise, along with avoiding caffeine, alcohol and large amounts of food prior to going to bed.[34] The principal investigator and student researcher(s) will recruit participants through flyers and word of mouth. Flyers will be placed at senior centers, community centers, and medical centers in Rapid City, SD. Interested participants will email or call [name] to enroll in the study. [name] will meet with the participant to determine eligibility status for the study. Due to the use of human subjects in this study, the research protocol will be approved by the University of South Dakota, Black Hills State University institutional review boards, and the National Institutes of Health prior to participant recruitment. Participant inclusion criteria will include participants ages 50-80, own a smartphone with the capability of receiving text messages. Exclusion criteria: a diagnosed sleep disorder such as insomnia or obstructive sleep apnea, and inability to wear any sleep tracking device on their wrist. During the initial visit, participants will read through and sign informed consent explaining the procedures and expectations of them during the study. The participants will then complete the following questionnaires related to the primary objectives of the study: the Ru-SATED questionnaire which includes the Sleep diary (based on the Consensus Sleep Diary) and Epworth Sleepiness Scale, Pittsburgh Sleep Quality Index, and the Sleep Hygiene Index. Participants will also complete the Perceived Stress Scale, Numeric Pain Rating Scale, and Patient Specific Functional Scale as secondary outcomes. Initial data collection will consist of taking anthropometric measurements and vital signs (Figure 1), with the assistance of the student researcher. The anthropometric measurements will include the following: body weight, height, and body mass index (BMI). BMI will be calculated by the standard method (body weight [kg]/height [m]) from weight and height measurements. The vital signs assessed will be resting blood pressure, heart rate, and respiratory rate. Following anthropometric data collection and vital signs, the participants will be instructed on the use of the wearable sleep tracker and provided assistance with setting up and charging the device. Participants will be instructed to contact the PI with any questions throughout the study by email or phone. The participants will then watch the sleep hygiene education video created by the research team.

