
Following the initial meeting with the PI, the participants will wear the sleep tracker on their wrist during the day and night for 4 weeks. The sleep tracker will monitor the physiological markers of sleep provided by wearable technology on sleep efficiency, time in bed, time actually sleeping, sleep midpoint, and time spent at each stage of sleep. Within the first week of participating in the study, student researcher(s) will contact the participant and perform a short 5- minute qualitative interview on the participants understanding and comprehension of the educational video along with a satisfaction survey (using a 5-point Likert scale). At the end of

the 4-week study period, the PI and/or student researcher(s) will once again meet with each participant. The participant will complete the following questionnaires once again: Sleep diary, Epworth Sleepiness Scale, Pittsburgh Sleep Quality Index, Sleep Hygiene Index, Perceived Stress Scale, Numeric Pain Rating Scale, and Patient Specific Functional Scale. Acceptability will be again assessed using a satisfaction survey (5-point Likert scale) and qualitative interview. Anthropometric data collection and vital signs will be reassessed, and the sleep tracker will be returned to the PI. Pre/post measurements will be compared and data analyses will be conducted using a 2x2 mixed factorial repeated measures ANOVA test. The PI will be assisted in the stats process by her mentor, [name] along with her peer in the psychology department at her university.

[figure not shown]
During the first year of this study, when in the treatment development phase, our primary outcomes for feasibility will be the following: recruitment (people enrolled from people contacted), retention and attrition (participants who complete the study and number who drop out), adherence (number of sessions attended and adherence to intervention protocol). Acceptability will be assessed using the satisfaction survey (5-point Likert scale) and qualitative interview. This information will be used to tailor the intervention to CDOA to further assess treatment effect in year two and three.

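### Aim 1 is stated as efficacy of the sleep hygiene video, but the readable text describes no group without the video, so the plan can estimate only uncontrolled change after it

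*Combined protocol and SAP*

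**What the plan says.** **Objective.** The opening summary states: "The proposed research project will evaluate the efficacy of sleep hygiene education on CDOA". The Aim 1 heading is "Evaluate the efficacy and feasibility of sleep hygiene education on CDOA", and its rationale begins: "Our first aim is to determine if sleep hygiene education can be beneficial in improving sleep health in the CDOA population". The summary also speaks more generally of the efficacy and effectiveness of two interventions.

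**Who gets the video.** The Aim 1 experimental design has consent, questionnaires, body measurements and vital signs, and instruction on the tracker. Then: "The participants will then watch the sleep hygiene education video created by the research team". No exception is described.

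**Groups.** Under Aim 2, random assignment comes after the video. The Figure 2 labels are a video group (n=15) and a video plus daily text group (n=15). The control group there gets no texts, but it has already seen the video.

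**Analysis.** The only analysis named is in the Aim 1 section: "Pre/post measurements will be compared and data analyses will be conducted using a 2x2 mixed factorial repeated measures ANOVA test". Its factors are not named.

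**Year one.** The same section makes recruitment, retention and adherence the primary feasibility outcomes, and says that treatment effect will be assessed further in years two and three.

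**The concern.** An efficacy statement about the video needs an estimate of what would have happened without it. Over four weeks, sleep and stress scores can move for other reasons: wearing a tracker, attending visits, answering the same questionnaires twice, or regression to the mean. With no group that lacks the video, such change cannot be told apart from a video effect.

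At stake is the Aim 1 efficacy conclusion only. A significant pre/post change could be reported as efficacy of the video when part or all of it is nonspecific.

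**Working it through.** **Inputs.** Groups and order of events: Aim 1 and Aim 2, Experimental design. Sizes: 80 completers and 100 recruited (Aim 1, Rationale); 15 + 15 (Figure 2 labels). The recruitment figure reproduces: 80/(1 − 0.20) = 100. The 80 itself rests on the median size (84) of earlier studies, so there is no power figure to reproduce. The 15 + 15 = 30 in Figure 2 does not match 80, so both sizes are carried below.

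**Step 1: what each contrast estimates.** Let μ = baseline mean, V = video effect, D = nonspecific change, T = added text effect.

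| Cell | Expected mean |
|---|---|
| Video, pre | μ |
| Video, post | μ + V + D |
| Video + texts, pre | μ |
| Video + texts, post | μ + V + D + T |

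- Group-by-time interaction: (V + D + T) − (V + D) = T.
- Change in the video-only group: V + D.
- Pooled time effect, equal arms: V + D + T/2.

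V and D appear only as a sum. The four cells have rank 3 for 4 unknowns. Adding a hypothetical no-video group (pre μ, post μ + D) raises the rank to 4, so the missing comparator is the cause, not the ANOVA.

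If Aim 1 is instead a separate single cohort, the cells are μ and μ + V + D: rank 2 for 3 unknowns, and the ANOVA has no between-subject factor. The result is the same under both readings, and more participants do not change it.

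**Step 2: what this could look like in practice.** The documents give no value for D, so this is illustration. Take V = T = 0, two-sided 0.05, and D in units of the SD of change. The chance of a significant pre/post change (noncentral t) is:

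| D | n = 30 | n = 80 |
|---|---|---|
| 0.1 | 8% | 14% |
| 0.3 | 36% | 76% |
| 0.5 | 75% | 99% |

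The larger sample makes the misreading more likely.

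**Step 3: which measures have a pre-video value.** The questionnaires, weight, BMI and vital signs are taken before the video and again at the end. Tracker measures are not: "Following the initial meeting with the PI, the participants will wear the sleep tracker on their wrist". In Table 1, regularity, timing, efficiency and duration come from the tracker, so 4 of the 6 composite domains have no described pre-video value. The satisfaction domain is an average diary score, and no run of pre-video nights is described for it.

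**Step 4: precision of the video-only change.** 95% CI half-width = t(0.975, df)/√n; detectable change is at 80% power, two-sided 0.05; both in change-SD units.

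| Participants used | df | Half-width | Detectable change |
|---|---|---|---|
| 15 (video only) | 14 | 2.145/3.873 = 0.55 | 0.78 |
| 30 (pooled) | 28 | 2.048/5.477 = 0.37 | 0.53 |
| 40 (video only, equal split of 80 assumed) | 39 | 2.023/6.325 = 0.32 | 0.45 |
| 80 (pooled) | 78 | 1.991/8.944 = 0.22 | 0.32 |
| 80 (separate Aim 1 cohort) | 79 | 1.990/8.944 = 0.22 | 0.32 |

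**The case against.** **Figure 1 is not shown.** It is the Aim 1 design diagram and could depict a comparator, and a 2x2 mixed ANOVA does imply two groups. This stands as a limit on certainty. A reader might infer that the trial definitely has no such group; the documents support only that none is described in the text. Against the objection, the Aim 1 procedure is written out in full with no comparator, and the two Aim 2 groups would supply the ANOVA's second factor.

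**Year one is a feasibility pilot.** This stands in part. Feasibility and acceptability, and the tailoring for later years that rests on them, do not depend on separating V from D, and no decision rule is tied to the pre/post change. But efficacy remains in the stated aim, and saying that effect will be assessed further later implies some assessment now.

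**The ANOVA is a sound choice.** Agreed for Aim 2. A reader might infer that the method is wrong; it is not. No other analysis of these groups would isolate the video either. The mismatch is between objective and design.

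**The earlier pilot.** The rationale cites a six-week study that "found significant changes in sleep quality, maladaptive sleep health behaviors, and daytime sleepiness compared to controls", and says "we wanted to explore if a one-time educational video would show similar findings as the recent 6-week" study. A reader might infer a planned replication of a controlled result. The text does not support that: the sentence explains why a single video was chosen, and no formal comparison is planned.

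**Contamination by the texts.** A reader might also infer that the Aim 1 estimate will include T/2. That needs a shared cohort and use of the pooled time effect, and the documents state neither.

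**Conclusion.** The point holds for the readable text and should be fixed. As described, the study can estimate the added effect of the texts by a randomised contrast, and 4-week change after the video without a control. It cannot estimate the effect of the video. This is structural: it needs no assumed effect size and holds at any sample size and under either cohort reading. It rests on the text describing the whole Aim 1 design. Confidence is high on the algebra and moderate overall, because Figure 1 cannot be seen and feasibility is primary in year one.

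**What to change.** 1. Restate the Aim 1 objective and conclusion as feasibility plus uncontrolled 4-week change after the video. Change the matching efficacy and effectiveness wording about the video in the opening summary too. If Figure 1 does show a no-video group, describe that group in the text instead.
2. Report Aim 1 change as the mean paired change with 95% CI in participants who had the video without texts (all participants if Aim 1 is a separate cohort). Apply it to the questionnaires, weight, BMI and vital signs. Leave out tracker measures and the 0–6 composite, and leave out the diary average unless pre-video nights are recorded.
3. Name the ANOVA factors: group (video versus video plus texts) and time (pre versus post). Keep causal language for the Aim 2 group-by-time contrast.

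**Cost.** Wording and analysis text only; the reported measures need no new data. Aim 1 makes a weaker claim. If the cohort is shared, leaving out the text group costs the precision shown in the last table: at the Figure 2 sizes, detectable change rises from 0.53 to 0.78 change-SD; with 80 split equally, from 0.32 to 0.45. If Aim 1 is a separate cohort, no precision is lost.

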**Figure 1: Study design for Specific Aim 1.**

**Specific Aim 2: Assess the ability of daily automated text messaging in CDOA to serve as an effective augmentation for sleep hygiene education.**

Rationale: Our second aim is to study the effectiveness of sending automated text messaging as an effective augmentation for sleep hygiene education in CDOA. With the promising short term results of a one-time sleep hygiene education session in young adults and the working adult population, we want to test if reinforcing the education daily through the use of a simple text message over the course of 4 weeks provides even greater and more sustainable results on changing people’s sleep behaviors. The expansion of smartphone technology combined with the abundance of services offering bulk messages to be sent out automatically provides an opportunity to reinforce the initial education with continual reminders of good sleep habits that an individual can practice over the course of 4-weeks. Given that 86% of adults over 50 now consistently use text messaging; it is safe to say this is an easy way to provide daily education and reminders on good sleep habits to this population.[28] If a new habit can be solidified during this timeframe, perhaps we will see long-term changes in sleep that will greatly improve overall health and wellness. For these reasons, we want to explore using automated text messaging as a supplement to our 30-minute educational video for sleep hygiene education.

Experimental design: Following anthropometric data collection and vital signs, as well as having the participants watch the sleep hygiene education video created by the research team, the participants will be randomly assigned to one of two groups (Figure 2). The intervention group will receive daily automated text messages scheduled for 8:00 pm every evening. The text messages will include a variety of sleep hygiene behavioral tips for the participant to try (Table 2). The participants will receive the text messages for a total of 4 weeks. The control group will not receive any intervention during this time frame. Following the 4 weeks, PI and student researcher(s) will meet again with the participants to collect the same data that was collected at the initial visit. Each participant will have a total of 2 sessions to complete with each session taking approximately 45-60 minutes to complete.

Sleep Hygiene Education Video Group

(n=15)

Sleep Hygiene Education Video Plus Daily  

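### Aim 2 states no analysis; if the plan's one ANOVA is meant to serve it, ANCOVA on the pre-randomisation questionnaires would usually estimate the text-messaging effect more precisely at almost no cost

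*Combined protocol and SAP*

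**What the plan says.** The Specific Aim 2 heading asks whether daily texts are able "to serve as an effective augmentation for sleep hygiene education". Its Experimental design says that, after body measurements, vital signs and the video, "the participants will be randomly assigned to one of two groups (Figure 2"). One group then receives a text each evening for 4 weeks; the other receives nothing further. The readable labels of Figure 2 show 15 in the "Sleep Hygiene Education Video Group" and 15 in the group that also receives texts. The section names no test, model, effect measure or covariate.

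The only analysis in the plan comes in the Specific Aim 1 Experimental design: pre and post measurements are compared, and "data analyses will be conducted using a 2x2 mixed factorial repeated measures ANOVA test".

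The same section fixes the order of measurement. At the initial visit, before the video, "The participants will then complete the following questionnaires related to the primary objectives of the study"; these include the Sleep Hygiene Index, the Pittsburgh Sleep Quality Index and the Epworth Sleepiness Scale. On the remaining three scales the plan adds: "Participants will also complete the Perceived Stress Scale, Numeric Pain Rating Scale, and Patient Specific Functional Scale as secondary outcomes". At 4 weeks "The participant will complete the following questionnaires once again", and the same scales are listed. The tracker differs: only after the initial meeting is it stated that "the participants will wear the sleep tracker on their wrist during the day and night for 4 weeks".

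The Specific Aim 1 Rationale sets a target of 80, raised to 100 for 20% dropout. The documents do not reconcile this with 15 per group.

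**The concern.** A 2x2 mixed ANOVA needs a two-level factor between persons and a two-level factor within persons. The readable Aim 1 text describes one programme with no comparator, so the only candidate for the first factor is the Aim 2 randomisation. This is an inference, and the figures cannot be seen beyond their labels. If it is right, the group-by-time term is the planned test of text messaging. With two groups and two times, that term is exactly the two-sample t-test on change scores.

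Subtracting the baseline fixes its coefficient at 1. ANCOVA estimates the coefficient, and so usually leaves less residual variance. Both are unbiased when the baseline is measured before randomisation.

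The ANOVA wording also leaves open which of its three tests answers Aim 2. The group main effect would be a poor choice: it averages in the pre-randomisation score, so its expected arm difference is only half the 4-week effect.

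Aim 2 holds the only randomised comparison in the plan. At 15 per group its intervals will be wide, and precision that costs nothing to collect is worth taking.

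**Working it through.** **The plan's own figure.** 80/(1 − 0.20) = 100, as the Specific Aim 1 Rationale states. The base of 80 rests on the sizes of earlier studies, not on a power calculation, so it supplies no SD, correlation or effect size.

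**Inputs.** From the documents: n = 15 per group (Figure 2). Two other sizes follow from stated figures: 15 × 0.8 = 12 completers per group if the 20% dropout applies to Figure 2, and 80/2 = 40 per group if the Aim 1 target were split equally. Assumed: pre/post correlation ρ from 0.3 to 0.9, equal SDs σ at both visits (relaxed below), and two-sided 95% intervals.

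**Formulas.**
- Change score: variance = 2σ²(1 − ρ)(2/n), with 2n − 2 degrees of freedom.
- ANCOVA: variance = σ²(1 − ρ²)(2/n)[1 + 1/(2n − 4)], with 2n − 3 degrees of freedom. The bracket is the cost of estimating the slope: 1.050 at n = 12, 1.038 at n = 15, 1.013 at n = 40.
- Ratio, ANCOVA to change score = [(1 + ρ)/2] × [1 + 1/(2n − 4)].

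**Example, n = 15 and ρ = 0.5.** Ratio = 0.75 × 1.038 = 0.779, a reduction of 22%. SEs are 0.365 (change score) and 0.322 (ANCOVA) in units of σ. Half-widths are 0.748 and 0.661.

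**Results at n = 15, equal SDs.**

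| ρ | Variance ratio | 95% CI half-width, change score → ANCOVA (SD) | Equivalent change-score n per group (15/ratio) |
|---|---|---|---|
| 0.3 | 0.675 | 0.885 → 0.728 | 22.2 |
| 0.5 | 0.779 | 0.748 → 0.661 | 19.3 |
| 0.7 | 0.883 | 0.579 → 0.545 | 17.0 |
| 0.9 | 0.987 | 0.335 → 0.333 | 15.2 |

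Simulation with 40,000 trials per setting gave ratios of 0.671, 0.775, 0.885 and 0.984.

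**Other sizes.** Ratios at the same four correlations are 0.683, 0.788, 0.893 and 0.998 at n = 12, and 0.659, 0.760, 0.861 and 0.962 at n = 40. At ρ = 0.5 the half-width goes from 0.847 to 0.753 SD at n = 12, and from 0.445 to 0.388 SD at n = 40.

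**Where the gain ends.** With equal SDs the variances are equal at ρ = 2/[1 + 1/(2n − 4)] − 1, which is 0.905, 0.926 and 0.974 at n = 12, 15 and 40.

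**Unequal SDs.** Let k be the 4-week SD divided by the baseline SD. At n = 15 the ratio is 1.038·k²(1 − ρ²)/(1 + k² − 2ρk):

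| ρ | k = 0.8 | k = 1.25 |
|---|---|---|
| 0.3 | 0.521 | 0.815 |
| 0.5 | 0.593 | 0.927 |
| 0.7 | 0.652 | 1.018 |
| 0.9 | 0.631 | 0.987 |

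The denominator equals k²(1 − ρ²) + (1 − ρk)², so the ratio cannot exceed the bracket. The largest possible loss is therefore 3.8% of variance at n = 15, reached when the slope ρk of 4-week score on baseline is 1.

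**Power, for scale.** At n = 15 and ρ = 0.5, power for an assumed effect of 0.8 SD rises from 0.56 to 0.67, and for 0.5 SD from 0.26 to 0.32.

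**The case against.** The strongest reply is that nothing here is broken. The 2x2 mixed ANOVA is a standard analysis of a two-arm pre/post design, its interaction test is valid, and the gain depends on a correlation the documents do not give. At ρ = 0.7 the half-width changes by about 0.03 SD, which would hardly alter the reading of a 30-person pilot. The plan also makes recruitment, retention and adherence the primary feasibility outcomes of year one and leaves further assessment of treatment effect to years two and three. The change misses the FitBit measures and the composite, and three of the six scales it covers are labelled secondary.

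Most of that stands as a limit on weight. It does not answer the point. The Aim 2 wording claims effectiveness and randomises for it, yet no analysis is stated whatever ρ may be. Once a sentence must be written, the model that usually gains and can lose at most 3.8% of variance at 15 per group is the better one to name.

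Three further objections are fair. The sleep diary, weight, BMI and vital signs are also collected at both visits. Six separate models raise multiplicity. Keeping a pre/post comparison for Aim 1 requires saying whether texted participants enter it, since pooling them would mix the video and text effects. These call for care in the wording; they do not undo the recommendation.

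**Conclusion.** The point holds as an improvement the plan should make, not as an error in it. Aim 2 has no stated analysis, and using the ANOVA for it is a reasonable inference. On that reading, ANCOVA lowers the variance of the text-messaging effect at 15 per group by 32.5% to 1% over correlations of 0.3 to 0.9 with equal SDs. The gain is larger if scores are less variable at 4 weeks than at baseline. It is smaller, or a slight loss, if they are more variable. It is usual, not guaranteed, and modest at this size: even with ANCOVA, power for 0.5 SD at ρ = 0.5 is about 0.32. The direction is the same at 12, 15 or 40 per group.

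The conclusion covers the Sleep Hygiene Index, Pittsburgh Sleep Quality Index, Epworth Sleepiness Scale, Perceived Stress Scale, pain scale and functional scale. It excludes the FitBit outcomes, and the 0–6 composite that takes four of its six domains from FitBit, because no wear before the intervention is described.

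**What to change.** Add an Aim 2 analysis statement. For each of the six questionnaires, fit 4-week score = arm + baseline score, and report the adjusted arm difference with its 95% CI as the test of text messaging, in place of the ANOVA group-by-time term or group main effect. Keep the within-person pre/post comparison for Aim 1 and say which participants enter it. Do not apply this model to the FitBit outcomes or the composite as the plan stands. Say either which questionnaire is primary for Aim 2 or that the six results are read as estimates without a confirmatory claim. Weight, BMI and vital signs can take the same model if they are to be compared between arms; the diary can too, if its baseline entries are complete before randomisation. Reconcile 15 per group with the target of 80.

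The cost is a few sentences and one degree of freedom per model. No new data are needed, because both methods use the same complete pre/post pairs. The downside is a trivial loss of precision if ρ exceeds about 0.93 at 15 per group with equal SDs or, more generally, if the slope on baseline is close to 1.

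### The only planned analysis, a pre/post 2x2 mixed ANOVA, by default drops anyone without a closing value and does not fit the FitBit outcomes, which have no pre value

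*Combined protocol and SAP*

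**What the plan says.** Specific Aim 1 (Experimental design) gives the whole analysis in one sentence: values before and after are to be compared, and "data analyses will be conducted using a 2x2 mixed factorial repeated measures ANOVA test". The between-participant factor is not named. The only two-group factor in the document is the random allocation to text messages or no text messages under Specific Aim 2, so that is the natural reading.

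On numbers, the Aim 1 Rationale says the programme "will be conducted among 80 CDOA, ages 50-80 using a 30-minute educational video" and adds: "Taking into account a potential dropout rate of 20%, the initial total number of participants to be recruited will be 100". Figure 2, under Aim 2, shows 15 participants in each randomised group, which is 30 in total.

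On timing, the initial visit ends with the education video: "The participants will then watch the sleep hygiene education video created by the research team". Only then does tracking start: "Following the initial meeting with the PI, the participants will wear the sleep tracker on their wrist during the day and night for 4 weeks". Questionnaires are completed at the initial visit and at 4 weeks, with nothing between. Return of the tracker is mentioned only at the 4-week visit.

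Table 1 takes four of the six sleep health domains (regularity, timing, efficiency, duration) from the FitBit. The other two come from the sleep diary and the Epworth scale. Dropouts appear elsewhere only as a feasibility count. The document states no analysis population, as-randomised rule, missing-data method or sensitivity analysis.

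**The concern.** There are two problems with one source: a two-occasion method is the only one offered for data of two different kinds.

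First, a standard pre/post mixed ANOVA uses only participants who have both values. With no other rule stated, the comparison of text messages with no text messages would be made among those who reach the closing visit, not among those randomised. Only one arm receives daily messages, so unequal dropout is plausible. If the people who leave also sleep differently, the arm difference is distorted.

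Second, the FitBit markers are a 4-week series that begins after the initial visit. They have no pre value for anyone, so the ANOVA as described cannot be applied to them. It also has no way to use two or three weeks of nights from someone who then leaves. These markers are the plan's objective sleep outcomes.

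**Working it through.** **Inputs from the document.** Target 80, dropout 20%, recruit 100 (Aim 1 Rationale); 15 per group (Figure 2); wear for 4 weeks after the initial visit (Aim 1 Experimental design). Alpha, power, effect size and SD are not given.

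**1. The plan's own figure.** 80 / (1 − 0.20) = 100, which matches. Expected leavers: 100 × 0.20 = 20, leaving 80. If Figure 2 gives the number enrolled: 30 × 0.20 = 6, leaving 24.

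**2. Precision ceiling.** Interval width varies as 1/√n.
- √(100/80) = 1.118
- √(30/24) = 1.118

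Intervals are therefore at most about 12% wider than with everyone fully observed, whichever sample size governs.

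**3. What FitBit data could be recovered.** Count participant-weeks and assume each leaver contributes 1 to 3 complete weeks.
- Completers: 80 × 4 = 320.
- Leavers at 1 week each: 20, which is 20/340 = 5.9% of all participant-weeks.
- Leavers at 3 weeks each: 60, which is 60/380 = 15.8%.

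The shares are the same with 24 completers and 6 leavers (6/102 and 18/114). Someone who leaves within the first week adds nothing to a weekly-mean model.

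**4. Possible bias (assumed values).** If leavers do worse than completers by δ SD and the dropout proportions are p_T (text) and p_C (control), the completer mean in each arm is too favourable by p × δ. The arm difference is therefore off by (p_T − p_C) × δ. With δ = 0.5:
- 25% v 15%: 0.10 × 0.5 = 0.05 SD
- 30% v 10%: 0.20 × 0.5 = 0.10 SD
- 20% v 20%: 0

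**5. Scale.** Assuming two-sided alpha 0.05, 80% power and equal arms, the detectable difference is (1.96 + 0.84) × √(2/n).
- n = 40 per arm: 0.63 SD
- n = 15 per arm: 1.02 SD

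A bias of 0.05 to 0.10 SD is 8% to 16% of the first and 5% to 10% of the second.

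**6. Fit of the method to each outcome.**
- Questionnaires: a pre and a post value exist, so the ANOVA can be run, on people with both.
- FitBit markers: only post-visit values exist, so there is no pre/post pair.
- Composite score (0 to 6): four domains lack a pre value, and the closing score also needs the diary and the Epworth scale.

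**The case against.** The strongest reply is that the document never says leavers are excluded, and this is correct. A reader might infer that the plan deliberately keeps only completers and discards FitBit nights it has already collected. The text supports neither. Completer-only analysis is the default behaviour of the named method, not a stated rule. The document does not say whether a leaver's FitBit data are retrieved or kept. Table 1 defines three FitBit domains as averages and regularity as a standard deviation, and all four could be computed from a shorter series.

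It is also fair to say that the lack of a FitBit pre value is a separate gap, so the ANOVA cannot be what discards those nights. That narrows the point but does not remove it. If the one stated method cannot be applied to the FitBit markers, those outcomes have no workable analysis, and a model of arm by week needs no baseline.

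Three further limits stand. For questionnaires there is no interim assessment, so modelling recovers almost nothing from people who leave. A weekly-mean model does not rescue the composite, or regularity, which is a spread across nights. A mixed model does not remove bias when dropout depends on sleep that was not observed.

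Finally, this is the first year of a pilot, with retention and attrition among its primary feasibility outcomes, so dropout will be reported. But reporting it does not deal with its effect on the comparison, and Aim 2 sets out to test whether text messages add to the education.

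**Conclusion.** The point holds in this form: the single stated analysis is complete-case by default, the plan itself expects 20% loss, no rule offsets it, and the method does not match the FitBit outcomes. It should be changed before analysis.

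The size is moderate and partly unknown. The loss is 20 of 100, or 6 of 30 if Figure 2 governs, and the document must reconcile the two. The 12% widening is an upper bound, because leavers can supply only part of their FitBit weeks and, under the current design, no closing questionnaire. The 0.05 to 0.10 SD shifts rest wholly on assumed dropout differences and an assumed deficit in leavers. A reader might infer that the arm comparison will be biased. The document does not show this, since it gives no dropout by arm, and equal dropout with equal deficits would give no shift.

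**What to change.** - **Continuous FitBit outcomes** (efficiency, time in bed, sleep time, midpoint, stage times): replace the ANOVA with a linear mixed model on weekly means, with arm, week, arm-by-week and a random participant effect. No FitBit baseline is required. Include every randomised participant with at least one week of data, in the assigned arm.
- **People who leave:** state that FitBit data recorded before leaving are retrieved and kept.
- **Questionnaires and composite:** analyse everyone with a closing response in the arm assigned. For questionnaires this will be nearly the same people as the ANOVA uses. Offering the closing set by web link or phone to those who miss the second visit would be the practical way to reduce the loss.
- **Sensitivity:** keep the completer ANOVA where a pre value exists.
- **Numbers:** reconcile 80 and 100 under Aim 1 with 15 per group in Figure 2, and name the between-participant factor.

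The cost is analysis-plan wording, a little more programming and, if adopted, a remote link. No extra participants or assessments are needed. The price is reliance on a missing-at-random assumption: the model reduces bias only where the observed data explain dropout.
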